9.1.1 Previous Study Period

Previous Study Period starts from the first dose date of study drug in the parent studies (109 and 011B) to up to the first dose date of study drug in Study 110, including 1) the planned 2-week washout period per Study 011B design; or 2) the Roll-Over Gap between the previous studies (Study 109 and Study 011B) and Study 110.

For the majority of the subjects, the first dose of study drug and assessments in Study 110 will happen on the same day as the Week 24 Visit in Study 109 or the Week 26 Visit in Study 011B.

For assessment performed on the first dose day in Study 110:

- If information regarding the assessment timing is available, then the assessment time will be compared to the first dose time in Study 110 to decide whether the assessment is before the first dose, concurrent with the first dose, or after the first dose.
- If information regarding assessment timing is not available, then the record will be included in the Previous Study Period if it comes from the Previous Study database, and the record will be included in the Current Study Period if it comes from the Current Study database.

Treatment-Emergent Period for the Previous Study Period

The treatment-emergent period for the Previous Study Period is the period on or after the first dose of study drug in the previous studies to 28 days after the last dose of the previous studies, or the last day of the Previous Study Period, or up to the first dose date in Study 110 (not including the first dose date in Study 110), whichever occurs first, for subjects dosed in Study 110.

For subjects not dosed in Study 110, the treatment-emergent period will be the period on or after the first dose of study drug in the previous studies to 28 days (inclusive) after the last dose of study drug in the previous studies or to the last day in the previous studies (inclusive), whichever occurs first.

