9.1.2 Current Study Period

Current Study Period starts from the first dose date of study drug in Study 110 to the last day in Study 110.

Treatment-Emergent Period for the Current Study Period

The treatment-emergent period for the Current Study Period is the period on or after the first dose of study drug in Study 110 to 28 days (inclusive) after the last dose of study drug in Study 110 or up to the last day in Study 110, whichever occurs first.

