9.1.3 Cumulative Study Period

Cumulative Study Period starts from the first dose of study drug in the parent studies (109 and 011B) to the last day in Study 110, regardless of whether there is 1) the planned 2-week washout period per Study 011B design; or 2) a Roll-Over Gap between the previous studies (Study 109 and Study 011B) and Study 110. For subjects not enrolled in Study 110, the Cumulative Study Period will be the same as the Previous Study Period.

Treatment-Emergent Period for the Cumulative Study Period

The treatment-emergent period for the Cumulative Study Period is the period on or after the first dose of study drug in the previous studies to 28 days (inclusive) after the last dose of study drug in Study 110, or up to the last day in Study 110, whichever occurs first. For subjects not enrolled in Study 110, the treatment-emergent period for the Cumulative Study Period will be the same as that of the Previous Study Period.

Handling of the data during the gap between previous studies (Study 109 and Study 011B) and the rollover study (Study 110)

There may be a Roll-Over Gap between the previous studies and the rollover study, defined as the time period between the Week 24 Visit of Study 109 or the Week 26 Visit of Study 011B and the date prior to the Day 1 Visit of Study 110. All analyses will be performed regardless of whether there is a Roll-Over Gap between the previous studies (Study 109 and Study 011B) and Study 110.

- This affects summary of the following possibly continuing events: 1) AEs; 2) CMs; and 3) Pulmonary Exacerbation related endpoints: Pulmonary Exacerbations, Pulmonary Exacerbations requiring hospitalizations (planned and unplanned), and Pulmonary Exacerbations requiring IV antibiotics.

Events that happen during the Roll-Over Gap will be included in the Cumulative Study Period related analysis, but not necessarily in the analysis of the previous studies or the Current Study Period for Study 110. There are possible differences between results from Cumulative Study Period and combining results from previous studies and the Study 110.

- The Roll-Over Gap will not be considered in the derivation of the analysis window. The assessments will be selected per windowing rules specified for visits in Study 110 as described in Appendix D. The same set of selected records will be associated with different visit labels for different dosing periods.

9.2 Treatment Cohort Period 2

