10.1.2 Safety Analysis Presentation Rules and Format

10.1.2.1 Event Data

Treatment Cohort Period 1

Unless otherwise specified, incidence tables summarizing n and percentages for categorical safety data will be provided for:

- Previous Study Period (Studies 109/011B) based on the Safety Set with two treatment groups (L200/I, Placebo);
- Current Study Period (Study 110) based on the 110 Safety Set with two treatment groups (L200/I-L/I, P-L/I) and Overall;
- Cumulative Study Period based on Safety Set with L200/I-L/I, and Current Study Period based on 110 Safety Set with P-L/I, pooled together. The pooled treatment group is presented as L/I Overall.

Exposure-adjusted number of events will summarize number of events per 100 patient-year (100PY) for AE related safety data. Note: 1 patient with 48 weeks of exposure duration is defined as 1 patient-year (1PY). The exposure-adjusted number of events will be provided for the Study Periods with the analyses sets and treatment groups as defined above.

The categorical safety summary tables with incidence only will be presented in the table format as shown in Table 10-3. The categorical safety summary tables with both incidence and

exposure-adjusted number of events summaries will be presented in the table format as shown in Table 10-4.

Table 10-3 Presentation Format for Summary Tables of Categorical Safety Endpoints with Incidence Summary Only

109/011B		110			109/011B and 110	
L200/I	Placebo	L200/I-L/I	P-L/I	Overall	L/I Overall	

Table 10-4 Presentation Format for Summary Tables of Categorical Safety Endpoints with Both Incidence and Exposure-Adjusted Number of Events Summaries

109/011B				110				109/011B and 110			
L200/I		Placebo		L200/I-L/I		P-L/I		Overall		L/I Overall	
n (%)	Events/100PY	n (%)	Events/100PY	n (%)	Events/100PY	n (%)	Events/100PY	n (%)	Events/100PY	n (%)	Events/100PY

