10.2.4 Study Drug Exposure

Treatment Cohort Period 1

Study drug exposure will be summarized for the Previous Study Period based on Safety Set, for the Current Study Period based on 110 Safety Set, and for the Cumulative Study Period based on Safety Set.

Duration of exposure is defined as: last available dose date of the Study Period – first dose date of the same Study Period + 1 day, regardless of 1) unplanned interruptions, 2) the Roll-Over Gap between Previous Study and Study 110 and 3) the 2-week planned wash-out period for subjects from Study 011B for the summary of study drug exposure for the Cumulative Study Period. Duration/cumulative duration of study drug exposure will be summarized descriptively as a quantitative variable (number, mean, SD, SE, median, min, and max) for:

- Previous Study Period (Studies 109/011B) based on Safety Set with two treatment groups (L200/I, Placebo);
- Current Study Period (Study 110) based on 110 Safety Set with two treatment groups (L200/I-L/I, P-L/I) and Overall;
- Cumulative Study Period based on Safety Set with L200/I-L/I, and Current Study Period based on 110 Safety Set with P-L/I, pooled together. The pooled treatment group is presented as L/I Overall.

Additionally, the total duration of study drug exposure, defined as the sum of the subject's duration of treatment exposure and expressed in patient years, will be provided.

Duration/cumulative duration of exposure will also be summarized as a categorical variable: ≥ 1 dose of study drug to <24 weeks, ≥ 24 to <48 weeks, ≥ 48 to <72 weeks, ≥ 72 to <96 weeks, ≥ 96 weeks to 120 weeks, and ≥ 120 weeks.

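### TEAE rates count events after last dose but person-time only to last dose, by amounts that differ between columns; separately, exacerbation censoring departs from the protocol for Study 109 completers not enrolled in Study 110

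*SAP*

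**What the plan says.** **Rate.** SAP 10.1.2.1 defines the measure: "Exposure-adjusted number of events will summarize number of events per 100 patient-year (100PY) for AE related safety data". Its note ties the denominator to drug exposure: "1 patient with 48 weeks of exposure duration is defined as 1 patient-year (1PY"). Table 10-4 prints the rate side by side for the 109/011B columns (L200/I, Placebo), the Study 110 columns and L/I Overall.

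**Numerator.** SAP 10.4.1 counts events that arise or worsen in the treatment-emergent period. In the Current Study Period that window runs "to 28 days (inclusive) after the last dose of study drug in Study 110 or up to the last day in Study 110", whichever is first. The Cumulative Study Period ends the same way: "to 28 days (inclusive) after the last dose of study drug in Study 110, or up to the last day in Study 110". For subjects dosed in Study 110, the Previous Study Period window can also be cut "up to the first dose date in Study 110 (not including the first dose date in Study 110), whichever occurs first".

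**Denominator.** SAP 10.2.4: "Duration of exposure is defined as: last available dose date of the Study Period", minus the first dose date, plus 1 day. For the cumulative summary this is regardless of "the 2-week planned wash-out period for subjects from Study 011B for the summary of study drug exposure for the Cumulative Study Period".

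**Protocol.** Sections 12.3 (28-day window), 12.4.2.4 (exposure to last dose) and 12.4.4.1 (events adjusted for exposure) specify the same combination.

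**Time to first exacerbation.** SAP 10.3.2.2.2 counts events after treatment discontinuation. Event-free Study 109 completers who did not enrol in Study 110 are censored at their last Study 109 dose. Protocol 12.4.3 censors event-free completers outside the Treatment Cohort at the end of the previous study's efficacy analysis period.

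**The concern.** A rate should divide events by the time over which those events could be counted. Here the days after last dose add events and no person-time. If that tail were the same fraction of exposure everywhere, it would scale all columns alike and do little harm. It is not the same, because the SAP's caps cut it to different lengths in columns that will be read against each other. Safety is the primary objective, and this rate is the only Table 10-4 measure that allows for unequal follow-up.

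The Kaplan-Meier rule has a related fault. For a subject who stopped drug early but stayed in Study 109, an exacerbation after stopping counts, while event-free time after stopping is discarded. That pushes the estimated incidence upward.

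**Working it through.** The plan states no events-per-100PY figure, so there is none to reproduce.

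**Inputs from the documents**
- About 200 subjects from Study 109 and 56 from Study 011B (SAP 7.2). All Study 011B subjects fall in L200/I (SAP Table 8-3).
- 24 weeks = 168 days of dosing in the previous study. Week 96 is study day 673 (SAP Appendix D), with the last dose at that visit.
- Gap after the previous study: "For the majority of the subjects, the first dose of study drug and assessments in Study 110 will happen on the same day" as the final visit of the previous study. This gives a tail of about 0 days for Study 109 and 14 days (the planned washout) for Study 011B.
- Safety Follow-up Visit at 28 ± 7 days (Protocol 8.1.1.2). With the 28-day cap, the Study 110 tail is 21 to 28 days.

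**Assumptions.** The event rate in the tail equals the on-drug rate. Study 109 allocation is not given, so I take Na = 80 to 130 of 200 on active drug.

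**Formula.** Printed rate / matched rate = 1 + (sum of unmatched days) / (sum of exposure days). The 48-week patient-year cancels.

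**Per subject**
- Study 011B, Previous Study Period: 14/168 = 8.3%
- Study 110 completer: 21/673 = 3.1% to 28/673 = 4.2%
- Cumulative, Study 109 active: exposure 168 + 673 = 841 days; 21/841 = 2.5% to 28/841 = 3.3%

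**By column**, for a matched rate of 100, same-day rollover, Na = 100, all completing Week 96 with a 28-day tail:

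| Column | Inflation | Prints as |
|---|---|---|
| 109/011B L200/I | 56×14 / (156×168) = 3.0% | 103.0 |
| 109/011B Placebo | 0 | 100.0 |
| Study 110 | 28/673 = 4.2% | 104.2 |
| L/I Overall | 256×28 / (56×855 + 100×841 + 100×673) = 3.6% | 103.6 |

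(855 = 168 + 14 + 673 for Study 011B.)

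**L200/I to Placebo ratio, same-day rollover:** 1 + 56×14 / ((56 + Na)×168) = 1.034, 1.030 and 1.025 for Na = 80, 100 and 130.

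**Is the sign fixed?** No. Suppose all 56 Study 011B subjects roll over the same day and 60% of Study 109 subjects have a gap of at least 28 days. Then (56 + 80)/256 = 53% are same-day, still a majority. The mean Study 109 tail is 0.6×28 = 16.8 days. Placebo is inflated by 16.8/168 = 10.0%, and L200/I by (56×14 + 100×16.8)/(156×168) = 9.4%. The ratio is 1.094/1.100 = 0.995. If all 127 gaps compatible with a majority fall in Study 109, the ratio is 0.992 to 0.994 for Na = 80 to 130. Unequal non-rollover does the same: with no gaps, nobody on active but 20% of placebo not dosed in Study 110, and a full 28-day tail, it is 1.0299/1.0333 = 0.997.

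**Against sampling error.** At an assumed 200 to 500 events per 100 calendar patient-years and Na = 100, the Poisson standard error of the L200/I to Placebo log ratio is about 8% to 13%. Overdispersion would enlarge it.

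**Kaplan-Meier.** Completers dosed to Week 24 took their last dose that day or the evening before (Protocol 8.1), so the two censoring rules differ by 0 to 1 day. A subject who stopped at Week 4 and stayed to Week 24 would lose up to 20 weeks under the last-dose rule. As an illustration, assume a constant hazard and that 5% to 10% of an arm stop between Weeks 4 and 12, stay to Week 24, and are censored at last dose if event-free. A true Week 24 incidence of 0.20 is then estimated as 0.204 to 0.215, and 0.30 as 0.306 to 0.319.

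**The case against.** The strongest defence is that this is a protocol convention and not a slip. The protocol prescribes events adjusted for total exposure, the SAP follows it and labels the measure accordingly, safety is descriptive only (SAP 10.4), and the repair puts off-drug days in the denominator. It stands that the SAP does not depart from the protocol here and that any repair must be recorded as a change. It does not make the columns comparable: the numerator already contains off-drug days, and the caps make their share unequal. The SAP already uses period-matched time in the negative binomial offset for exacerbations.

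Three stronger readings are tempting and fail:
- *L200/I must print above Placebo, because only L200/I contains washout time.* This holds under same-day rollover. The stated majority is pooled over both studies, and the counter-examples above go below 1.
- *The washout is handled inconsistently, counted as exposure in one column and not in another.* One formula applies throughout. In the cumulative period the washout lies between doses; in the Previous Study Period it follows the last dose.
- *The last-dose rule shortens follow-up for all Study 109 completers.* It covers only those not enrolled in Study 110. For Observational Cohort subjects, either the rule does not reach them and none exists, or it is extended to them and loses their off-drug time. Both cannot be charged at once.

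**Conclusion.** The mismatch is plain in the text and modest in size. In the 109/011B comparison it is worth about 2.5% to 3.4% under same-day rollover and equal true rates. Neither size nor sign is fixed once gap shares or non-rollover differ between studies or arms. It lies within sampling noise for L200/I versus Placebo and would not by itself change a descriptive conclusion. The figures rest on the assumed Study 109 allocation and an equal event rate in the tail.

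One length is open. Subjects moving straight to commercial drug need no Safety Follow-up Visit (Protocol 8.1.1.3), yet AEs are collected to 28 days for enrolled subjects without one (Protocol 13.1.1.3). The last day in Study 110 is not defined, so their tail could be anything from 0 to 28 days. For Treatment Cohort Period 2 entrants, SAP 9.2 indicates where Period 1 ends.

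The Kaplan-Meier conflict is real but narrow. It matters only for subjects who stopped early and stayed in Study 109; Protocol 9.1 admits such subjects to the Observational Cohort, but their number is unknown. Neither SAP censoring rule covers that cohort, although the protocol rule does. The end of the Study 109 efficacy analysis period is not defined in these documents.

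**What to change.** 1. In SAP 10.1.2.1, divide TEAE counts by treatment-emergent person-time, with the same start and cut-off dates as the numerator (SAP 9.1.1 to 9.1.3). Matching removes the artefact for any gap pattern.
2. Define the last day in Study 110, notably for subjects moving to commercial drug, and keep it consistent with SAP 9.2 for Period 2 entrants.
3. Record this as a change from Protocol 12.4.4.1. Keep the SAP 10.2.4 definition for the exposure table.
4. In SAP 10.3.2.2.2, apply the Protocol 12.4.3 censoring to every event-free Study 109 subject outside the Treatment Cohort, including the Observational Cohort: at withdrawal, or at the end of the Study 109 efficacy analysis period for completers. State that end date.

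The cost is SAP wording and derived date variables; no new data are needed. If interim tables used the exposure denominator (their plans are separate, SAP 11.1), final rates will not line up with them and a footnote is needed.

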12.4.4.1 Adverse Events

For the Observational Cohort, a summary table will be presented for all SAEs.

For the Treatment Cohort, TEAEs will be summarized for current dosing period based on Study 110 Safety Set, and for the active dosing period based on Integrated Safety Set.

For analysis purposes, AEs will be classified as pretreatment AEs, TEAEs, or post-treatment AEs.

- **TEAE:** any AE that increased in severity or newly developed during the treatment-emergent period.
- **Post-treatment AE:** any AE that increased in severity or newly developed after the treatment-emergent period.

Handling of AEs, that are ongoing or newly developed at, or after, the completion of treatment in Study 109 and Study 011B through the initial dose of study drug administration in Study 110, will be detailed in the SAP.

For AEs with missing or partial start dates, if there is no clear evidence that the AEs started before the current study treatment, then the AEs will be classified as TEAEs.

An overview of the TEAE profile will be provided, including total number of TEAEs, with number and percentage of subjects for the following categories: (1) All TEAEs, (2) Grades 3/4 TEAEs, (3) TEAEs by relationship, (4) TEAEs by maximum severity, (5) TEAEs leading to treatment interruption, (6) TEAEs leading to treatment discontinuation, (7) Serious TEAEs, (8) Related serious TEAEs, and (9) TEAEs leading to death. A summary of number and percentages of subjects, as well as number of events per 100 patient-years (number of events adjusted for the total duration of exposure), will be provided.

AE summary tables will be presented for TEAEs and will include the following:

- All TEAEs
- Grades 3/4 TEAEs
- TEAEs by relationship

- TEAEs by maximum severity
- TEAEs leading to treatment interruption
- TEAEs leading to treatment discontinuation
- Serious TEAEs
- Related serious TEAEs
- TEAEs leading to death
- Frequently reported TEAEs

Summaries will be presented by MedDRA system organ class and preferred term (PT) using number and percentages of subjects as well as number of events per 100 patient-years (number of events adjusted for the total duration of exposure). When summarizing the number and percentage of subjects with an event, subjects with multiple occurrences of the same AE or a continuing AE will be counted once. Only the maximum severity level will be presented in the severity summaries and the worst/highest relationship level in the relationship summaries.

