5 STUDY OBJECTIVES

5.1 Primary Objective

To evaluate the long-term safety and tolerability of lumacaftor in combination with ivacaftor in subjects aged 6 years and older with CF, homozygous for the *F508del-CFTR* mutation, who are in the Treatment Cohort Period 1.

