10.4.1 Adverse Events

Observational Cohort

For the Observational Cohort, a listing will be presented for all SAEs.

Treatment Cohort Period 1

For Treatment Cohort Period 1, TEAEs will be summarized following the presentation format in Section 10.1.2.1, Table 10-3.

- 1) Previous Study Period based on Safety Set by treatment groups (L200/I and Placebo);
- 2) Current Study Period based on 110 Safety Set by treatment groups (L200/I-L/I and P-L/I) and Overall;
- 3) Cumulative Study Period based on Safety Set with L200/I-L/I, and Current Study Period based on 110 Safety Set with P-L/I, pooled together. The pooled treatment group is presented as L/I Overall.

In TEAE summaries, number and percentage of subjects, as well as exposure-adjusted number of events, will be provided.

For analysis purposes, AEs will be classified as pretreatment AEs, TEAEs, or post-treatment AEs.

- **Pretreatment AE:** any AE that started in the pre-treatment period. The pre-treatment AE will be the same for Previous Study Period and Cumulative Study Period.
- **TEAE:** any AE that increased in severity or that was newly developed in the treatment-emergent period.
- **Post-treatment AE:** any AE that increased in severity or that was newly developed in the post-treatment period.

For AEs with missing or partial start dates, if there is no clear evidence that the AEs started before or after study treatment, then the AEs will be classified as TEAEs. Details regarding handling rules of missing dates are included in Appendix J.

An overview table of the TEAE profile for Treatment Cohort Period 1 will be provided, including total number of TEAEs, with number and percent of subjects and exposure-adjusted number of events in 100PY for the following categories:

- All TEAEs
- Grade 3/4 TEAEs
- TEAEs by relationship
- TEAEs by maximum severity
- TEAEs leading to treatment interruption
- TEAEs leading to treatment discontinuation

- Serious TEAEs
- Related serious TEAEs
- TEAE leading to death

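### AE rates in the 96-week and pooled columns are single period averages, so for most adverse events they cannot separate early from late risk on drug; one table by time since first LUM/IVA dose would do so.

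*SAP*

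**What the plan says.** The primary objective is long-term safety: "To evaluate the long-term safety and tolerability of lumacaftor in combination with ivacaftor" (SAP 5.1). SAP 10.1.2.1 fixes the rate metric for AE data: "Exposure-adjusted number of events will summarize number of events per 100 patient-year (100PY) for AE related safety data", with 48 weeks of exposure counted as one patient-year. SAP 10.4.1 applies it: "In TEAE summaries, number and percentage of subjects, as well as exposure-adjusted number of events, will be provided". The protocol describes the same quantity as the "number of events adjusted for the total duration of exposure" (Protocol 12.4.4.1).

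Table 10-4 sets out the columns. The parent-study pair (L200/I and Placebo) comes first. Next is the "Current Study Period (Study 110) based on the 110 Safety Set with two treatment groups (L200/I-L/I, P-L/I) and Overall". Last comes the cumulative period for children who started on active drug, combined with the Study 110 period for those who started on placebo: "The pooled treatment group is presented as L/I Overall".

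Some information on AE timing is planned. SAP 10.4.1 summarises time to first onset and duration for three AESI groups (elevated transaminases, respiratory symptoms, respiratory events). TEAEs in Treatment Cohort Period 2 (France only, after Week 96) are summarised separately. SAP 10.2.4 bands duration of exposure in 24-week steps, but the bands are not carried over to AEs.

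**The concern.** Events per 100PY is the average of the event rate over whatever time the column covers. Two columns can be compared directly only if the rate is constant over time on drug. Here the columns cover different stretches of treatment, and two of them (Overall and L/I Overall) merge children at different stages.

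A long-term safety study has to show whether risk falls after the start, stays level or rises with longer exposure. In a 96-week column, a short burst of events at the start is spread over the whole period, and a rise in the second year is averaged with the first. For children who started on placebo, the P-L/I column is their only experience on active drug, and it is not split at all.

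**Working it through.** **1. The plan's own figure.** The only planning figure is SAP Table 7-1 (n = 256), and it reproduces as p ± 1.96·√(p(1−p)/256). For p = 0.2 this is 0.2 ± 1.96 × 0.025 = (0.151, 0.249). The other three rows also match to three decimals. It concerns cumulative incidence and has no time dimension.

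**2. Time on LUM/IVA in each column**, from 24 weeks in the parent studies and dosing to Week 96 in Study 110:

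| Table 10-4 column | Weeks on LUM/IVA | Length (weeks) |
|---|---|---|
| 109/011B L200/I | 0-24 | about 24 |
| 109/011B Placebo | none | about 24 |
| 110 L200/I-L/I | about 24-120 | about 96 |
| 110 P-L/I | 0-96 | about 96 |
| 110 Overall | the two above, merged | about 96 |
| L/I Overall | 0-120 pooled with 0-96 | up to about 120 |

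**3. Opposite profiles, same average (assumed rates per 100PY, 96 weeks).**
- Early harm: (4 × 500 + 92 × 100)/96 = 116.7.
- Late harm: (72 × 100 + 24 × 166.7)/96 = 116.7.

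**4. Dilution over a range.** If the rate is k times background for w weeks of a T-week column, the column shows a ratio of 1 + (k−1)w/T.

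| Assumed excess | T = 24 | T = 96 | T = 120 |
|---|---|---|---|
| 2× for first 2 weeks | 1.08 | 1.02 | 1.02 |
| 3× for first 4 weeks | 1.33 | 1.08 | 1.07 |
| 5× for first 4 weeks | 1.67 | 1.17 | 1.13 |
| 10× for first 8 weeks | 4.00 | 1.75 | 1.60 |
| 2× in last 24 weeks | – | 1.25 | 1.20 |
| 3× in last 24 weeks | – | 1.50 | 1.40 |

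For L/I Overall, assume 100 of the 200 Study 109 children were on active drug and follow-up is full. Exposure is (156 × 120 + 100 × 96)/48 = 590 PY. The 5×, 4-week case then gives 1 + (4 × 4 × 256)/28,320 = 1.145. With 80 to 120 on active drug, exposure is 580 to 600 PY and the ratio 1.147 to 1.142.

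**5. What the existing columns do show**, on the same 156/100 split with an assumed background of 10 per 100PY:

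| Assumed scenario | L200/I (0-24) | 110 L200/I-L/I | 110 P-L/I | L/I Overall |
|---|---|---|---|---|
| One extra event in 20% of children soon after starting | 10 + 0.20/0.5 × 100 = 50 | 10 | 10 + 0.20/2 × 100 = 20 | 10 + 51.2/590 × 100 = 18.7 |
| Rate doubles after week 72 on drug | 10 | (48 × 10 + 48 × 20)/96 = 15 | (72 × 10 + 24 × 20)/96 = 12.5 | 13.5 |

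The last cell is [156 × (72 × 10 + 48 × 20) + 100 × (72 × 10 + 24 × 20)]/28,320. Children who started on active drug show the change (50 then 10, or 10 then 15), but the 15 does not say when in the 96 weeks the rate rose. P-L/I gives one number in each case.

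**6. Can the split be supported?** With 256 dosed, no dropout, and an exact Poisson 95% CI for a true rate of 20 per 100PY:

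| Interval (weeks) | Exposure (PY) | Events | 95% CI per 100PY |
|---|---|---|---|
| 0-4 | 256 × 4/48 = 21.3 | 4 | 5.1-48.0 |
| >4-24 | 256 × 20/48 = 106.7 | 21 | 12.2-30.1 |
| each 24-week band to week 96 | 256 × 24/48 = 128 | 26 | 13.3-29.8 |
| >96-120 | 156 × 24/48 = 78 | 16 | 11.7-33.3 |

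The last interval holds 68 to 88 PY if 80 to 120 Study 109 children were on active drug.

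**The case against.** A reader might infer that the plan contains no AE timing at all. It does contain some. The AESI groups, which include the respiratory events most readily linked with starting drug, have a time-to-first-onset summary. Table 10-4 itself places weeks 0-24 on L200/I beside concurrent placebo and then shows the same group's later experience. Step 5 shows that a marked initiation effect would be visible there.

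A reader might also take L/I Overall against the 24-week placebo column as the main comparison (18.7 against 10 in step 5). Nothing in the SAP gives L/I Overall that status or plans that contrast; safety is descriptive only (SAP 10.4), and the more informative L200/I and Placebo columns stand next to each other.

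Nor are late harms hidden across the whole primary endpoint. Continuous laboratory values, ECG, vital signs, oximetry and predose spirometry are shown by visit, and slit-lamp shifts at each scheduled time point. Serious events and discontinuations are listed individually. Dilution affects rates, not the cumulative n (%) printed beside them. That the SAP expects start-of-treatment events is likewise an inference from the monitoring schedule, not something it states.

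These points limit the concern but do not remove it. The onset summary covers first events in three AESI groups and gives no rate by interval. The two-column split is coarse, applies only to children who started on active drug, and its second part includes only those who rolled over. Cumulative percentages over unequal durations are not comparable either. Part of the text after the LUM 400 mg TEAE overview in SAP 10.4.1 is redacted, and the interim-analysis SAPs are separate documents, so the statement is confined to what is visible.

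**Conclusion.** The point holds in limited form, as an inexpensive improvement. For general TEAEs, serious TEAEs and TEAEs leading to discontinuation, neither the 96-week P-L/I and L200/I-L/I columns nor the pooled Overall and L/I Overall columns can by themselves separate early from late risk on drug. Initiation risk in children who started on placebo, and any change in risk after week 24 in either group, cannot be located.

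The size depends on assumed rates, since the documents give none. A five-fold excess over 4 weeks reads as 1.67 in a 24-week column, 1.17 in a 96-week column and about 1.14 to 1.15 in L/I Overall. A doubling in the last 24 of 96 weeks reads as 1.25. The pooled figures further assume that all 256 eligible children are dosed, full follow-up, and 80 to 120 of the 200 Study 109 children on active drug.

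**What to change.** Add to SAP 10.4.1 one table set covering TEAEs, serious TEAEs, TEAEs leading to discontinuation and each AESI group, by interval since first LUM/IVA dose.

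- Use the 24-week bands of SAP 10.2.4, with the first band split (for example 0-4 and >4-24 weeks). Without that split, a 4-week, five-fold excess would still read as 1.67.
- Count time from the parent-study first dose for L200/I-L/I and from the Study 110 first dose for P-L/I.
- In each interval give children at risk, exposure and events per 100PY.
- Footnote that later intervals contain only children still on drug; that the 0-4 week interval (about 21 PY) and the >96 week interval (about 68 to 88 PY, on the assumptions above) are imprecise; and that the placebo column is comparable only with the first 24 weeks.
- State how many events in the first interval have an imputed onset, because SAP Appendix J moves some partial start dates to the first dose date.

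The cost is SAP wording and one table set from data already collected. The downside is that the late intervals are selected and sparser, which the footnotes disclose.
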